16.2.1.5 Sum of Longest Diameters (SOLD)

The sum of longest diameters of viable target lesions is collected on the "Sum of Longest Diameters" eCRF page. The relative change in SOLD of target lesions from baseline will be calculated as follows:

((SOLD of the target lesions at post-baseline – SOLD of target lesions at baseline) / SOLD of target lesions at baseline) *100

The relative change from baseline of SOLD in target lesions as well as occurrence of initial progressive disease with rationale evaluation type (target lesion/non-target lesion/new lesion) will be displayed against time point (weeks since treatment initiation) in a spider plot. The baseline relative change is considered "0" on day 1. Dose level and c-Met status (IHC/ISH) will be distinguished by different colors, line types, and/or symbols. Reference lines at +20% and -30% will be shown.

Best relative change in SOLD of target lesions from baseline will be calculated as follows for all subjects that present a measurable tumor at baseline and at least one post-baseline tumor assessment:

((the lowest SOLD of target lesions at post-baseline – SOLD of target lesions at baseline) / SOLD of target lesions at baseline) *100

The best relative change from baseline in SOLD will be displayed using waterfall plots. One plot will be color coded for dose level and c-Met status (IHC) and one will be color coded for dose level and c-Met status (ISH). Reference lines at +20% and -30% will be shown.

Summary statistics for the SOLD values and their change from baseline over time will be presented by the following in separate tables:

- Dose level and overall
- c-Met status (IHC), dose level, and overall
- c-Met status (ISH), dose level, and overall

If sufficient HGF data is available, scatter plots of baseline HGF (both CAF and cytoplasmic) versus the best (minimum) on treatment SOLD value by dose level will be presented.

SOLD data including absolute and relative change from baseline values will be listed.

16.2.1.6 Biological Response

Biological response is defined as the proportion of subjects with a decrease in AFP level of more than 20% at the Cycle 3 assessment, or the last assessment for subjects that terminated treatment prior to the Cycle 3 assessment, as compared with baseline. AFP level is measured at screening, Cycle 1 Day 1 (only if the screening measurement was done more than 7 days prior), Day 1 of every cycle thereafter, and the End of Treatment visit.

Biological response will be summarized, including corresponding two-sided exact Clopper-Pearson (2) 90% CIs, by the following in separate tables:

- Dose level and overall
- c-Met status (IHC), dose level, and overall
- c-Met status (ISH), dose level, and overall

If sufficient HGF data is available, scatter plots of best (minimum) on treatment AFP value versus both baseline HGF (CAF and cytoplasmic) will be provided.

Biological response will be flagged on the tumor marker listing. (See Section 17.3.)

16.2.2 Pharmacokinetics

Analysis Set: PK

Tepotinib and metabolite (MSC2571107A and MSC2571109A) concentrations in plasma will be listed and presented in tables and descriptively summarized by dose level, day and scheduled time point using N, arithmetic mean, standard deviation, standard error of the mean (SEM), median, minimum, maximum, and coefficient of variation (CV) (%). For descriptive statistics of concentration data, values below the lower limit of quantification (LLOQ) will be assigned values as defined in 16.2.2.2. Descriptive statistics of PK parameters will additionally show the geometric mean (GeoMean), the geometric CV percentage (GeoCV%), and the 95% CI for the geometric mean.

Individual plasma concentration-time profiles (linear and semi-logarithmic scales) will be plotted by dose level and day, overlaying tepotinib and its metabolites (i.e. all three analytes) in one plot per subject. Spaghetti plots overlaying all subjects' individual analyte concentrations (linear and semi-logarithmic scales) will be plotted by dose level and day for each of the three analytes separately. Mean plasma concentrations of all three analytes overlaid will also be plotted by dose level and day on linear (±standard deviation) and semi-logarithmic scales using schedule time points. Mean concentration time profiles per each analyte separately and by dose level will also be displayed, overlaying both Day 1 and Day 15 in one plot.

A listing of PK blood sample collection times by individual as well as derived sampling deviations will be provided.

PK profiles of tepotinib and its active metabolites (MSC2571107A, MSC2571109A) from study EMR200095-005 phase Ib part will be analyzed jointly with data from studies EMR200095-001, -002, -003, -004, -006 and -007 by a non-linear mixed effect approach. The plasma concentration time profiles after single or multiple dose administration of tepotinib in healthy volunteers and solid tumor patients will be evaluated with compartment models. Covariates of demographics, lab values, disease status and co-medication will be tested in order to identify any intrinsic and extrinsic factors that are predictive of PK inter-individual variability. More details are given in a separate Data Analysis Plan for Pooled Population Pharmacokinetic Analysis. The results will be reported separately.

16.2.2.1 Pharmacokinetic Endpoints

The following pharmacokinetic endpoints will be analyzed:

 Plasma PK parameters of tepotinib and metabolites MSC2571107A and MSC2571109A: the definition of the parameters and the planned analysis is described in the subsequent sections

16.2.2.2 Estimation of Individual Pharmacokinetic Parameters

Pharmacokinetic parameters will be calculated by the PPD PK group using standard non-compartmental methods, actual elapsed sampling times, and the actual administered dose. The PK parameters listed below will be calculated for tepotinib and metabolites MSC2571107A and MSC2571109A in plasma, when applicable, based on frequent PK sampling as applied in phase Ib. PK parameters will be summarized by PK analyte, dose level, and day.

C_{max}	Maximum observed concentration
t_{max}	Time of C_{max}
$\mathrm{AUC}_{0 ext{-t}}$	Area under the concentration-time curve from time zero to the last quantifiable concentration
t_{lag}	t_{lag} is the time prior to the first quantifiable (non-zero) concentration [for Cycle 1 Day 1 only]
C_{av}	The average concentration at steady state, calculated on Cycle 1 Day 15 only. $C_{av} = AUC_{\tau}/\tau$ (AUC _{0-t} if necessary).
C_{\min}	The minimum observed concentration during a complete dosing interval, calculated on Cycle 1 Day 15 only
AUC_{τ}	The area under the concentration-time curve over the dosing interval from $T_1=0$ h (predose) to $T_2=\tau$ h. Calculated using the mixed log linear trapezoidal rule (linear up, log down).

For Cycle 1 Day 1, AUC τ will be calculated as a partial area within the defined time range. For Cycle 1 Day 15, AUC τ will be calculated at steady state from the pre-dose time point to the dosing interval time. AUC τ will be calculated based on the observed concentration at the actual observation time, as long as actual time deviation is less than +/-10% at τ . If actual time deviation is equal to or greater than 10%, AUC τ will be reported as missing.

AUC_{0-t}/Dose Dose-Normalized AUC_{0-t}. Normalized using actual dose.

AUC_τ/Dose Dose-Normalized AUC_τ. Normalized using actual dose.

C_{max}/Dose Dose-Normalized C_{max}, Normalized using actual dose.

PTF The peak trough fluctuation ratio within a complete dosing

interval at steady state in %, calculated on Cycle 1 Day 15

only. PTF = $100*(C_{max}-C_{min})/C_{av}$

Potential drug accumulation will be evaluated by means of individual accumulation ratios for AUC_{τ} and C_{max} ($R_{acc(AUC)}$ and $R_{acc(Cmax)}$ respectively, that will be calculated by dividing the values obtained after multiple dose [e.g. on Cycle 1 Day 15] by the values obtained after single dose [e.g. Cycle 1 Day1]) and summarized descriptively for each dose level.

Individual metabolite to parent ratios for AUC_{0-t} and C_{max} ($MR_{(AUC0-t)}$ and $MR_{(Cmax)}$ respectively), will be calculated by dividing the value obtained for each metabolite by the value obtained for the parent (i.e. MSC2571107A/tepotinib and MSC2571109A/tepotinib), separately for single dose (e.g. Cycle 1 Day1) and multiple dose (e.g. Cycle 1 Day 15), and summarized descriptively for each dose level and day.

The dosing and sampling scheme in this study does not allow the reliable estimation of λ_z , considering the apparent terminal half-life of tepotinib and its metabolites. Therefore, all PK parameters dependent on λ_z will not be determined, i.e. $AUC_{0-\infty}$, % AUC_{extra} , CL/F; $t_{1/2}$, Vz/F, and Vss/F.

Other parameters may be added as appropriate.

The calculation of the AUCs will be performed using the mixed log-linear trapezoidal method (linear up, log down). The actual (unrounded) time of blood sampling will be used for PK evaluation. In cases where the actual sampling time is missing, calculations will be performed using the scheduled time. Otherwise, there will be no further imputation of missing data. The pre-dose samples will be considered as if they had been taken simultaneously with the administration. Plasma concentrations below LLOQ before the last quantifiable data point will be taken as zero for calculating the AUC (ie, embedded BLQ values will be set to zero). Plasma concentrations below LLOQ after the last quantifiable data point will be set to 'zero'.

PK parameters will be evaluated and listed for all subjects who provide sufficient concentrationtime data. Formal statistical hypotheses have not been planned for PK parameters. Any statistical tests that might be performed will be considered exploratory.

Dose proportionality will be presented graphically by day as follows:

- Boxplots for dose-normalized PK parameters (AUC_τ/Dose and C_{max}/Dose) by dose level
- Scatter plots on individual AUC_{τ} and C_{max} versus Dose on a linear scale.

PK Parameters are to be rounded for reporting as appropriate. In export datasets, PK parameters will be provided with full precision, and will not be rounded.

The Phoenix WinNonlin NCA Core Output will be provided in a separate listing.

17 Safety Evaluation

Analysis Set: ITT/SAF

The subsections in this section include specifications for summarizing safety endpoints that are common across clinical trials such as adverse events, laboratory tests and vital signs. The analysis for the primary endpoint, incidence of DLTs during Cycle 1, is specified in Section 16.1.

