### 7.1.3 Treatment Period

MSC2156119J will be administered once daily over a 21 day cycle until PD, or intolerable toxicity, death, or withdrawal from treatment.

## 7.1.3.1 Cycle 1 Day 1

The following assessments and examinations will be performed on this day:

- Optional tumor biopsy, excluding fine needle aspiration and cytology samples (frozen; for Pd/PK; may be taken either at screening or pretreatment on Cycle 1 Day 1; Phase Ib only; subjects who will have the optional biopsy should also have an on-treatment biopsy on any day from Cycle 1 Day 15 through Cycle 3 Day 1 [frozen, paired biopsy]);
- Tumor assessment by F-fluoro-D-glucose (FDG) positron emission tomography (PET) CT scan (predose only);
- Blood samples for CCI and Pd (predose only);
- CCI
- A urine pregnancy test will be completed in women of childbearing potential before administration of the dose. If the pregnancy test is positive, it must be confirmed with a serum pregnancy test.
- ECG [predose and at 4, 10, and 24 hours postdose for Phase Ib (the 24-hour postdose ECG is to be performed predose on the following day), and predose and at 4 hours postdose for Phase II]. ECGs will be performed immediately before PK sampling at times when both procedures are performed;
- PK blood samples [predose and at 0.25, 0.5, 1, 2, 4, 8, 10, and 24 hours postdose for Phase Ib (the 24-hour postdose PK blood sample is to be drawn predose on the following day); CCI
- AE assessment;
- Recording of concomitant medications/procedures;
- FHSI-8 and FACT-HP (Phase II only).

Additionally, the following assessments will be performed if the last assessments of these parameters were performed > 7 days prior to this visit:

• Viral load of HBV (for subjects with hepatitis B at screening) and viral load of HCV (for subjects with hepatitis C at screening);

- Physical examination including body weight;
- ECOG PS;
- Vital signs; blood samples (to assess hematology, chemistry, and coagulation);
- Urinalysis;
- Serum AFP.

## 7.1.3.2 Cycle 1 Day 2 and Cycle 1 Day 8

The visit on Cycle 1 Day 8 may be performed within  $\pm$  1 day of Cycle 1 Day 8. The following assessments and examinations will be performed on the days of these visits:

- Physical examination including body weight;
- Vital signs;
- Blood samples (to assess hematology, chemistry, and coagulation);
- AE assessment;
- Recording of concomitant medications/procedures.

# 7.1.3.3 Cycle 1 Day 15

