This visit may be performed within  $\pm 2$  days of Cycle 1 Day 15. The following assessments and examinations will be performed on this day:

- Physical examination including body weight;
- ECG [predose and at 4, 10, and 24 hours postdose for Phase Ib (the 24-hour postdose ECG is to be performed predose on the following day), and predose and at 4 hours postdose for Phase II]. ECGs will be performed immediately before PK sampling at times when both procedures are performed;
- PK blood samples (predose and at 0.25, 0.5, 1, 2, 4, 8, 10, and 24 hours postdose; Phase Ib only; the 24-hour postdose PK blood sample is to be performed predose on the following day);
- Blood samples (to assess hematology, chemistry, and coagulation);
- AE assessment;
- Recording of concomitant medications/procedures;
- Optional tumor biopsy, excluding fine needle aspiration and cytology samples (optional frozen sample for subjects who had the optional frozen pretreatment biopsy; this biopsy may be taken on any day from Cycle 1 Day 15 up through Cycle 3 Day 1; Phase Ib only);
- Blood sample for evaluation of CC

# 7.1.3.4 Cycle 2 Day 1

This visit may be performed within  $\pm 5$  days of Cycle 2 Day 1. Efforts should be made to strictly maintain the schedule defined in the protocol. Cycle 1 Day 1 should be used as a reference to calculate Day 1 of all subsequent cycles even in the case of treatment or visit delays.

The following assessments and examinations will be performed on this day:

- Physical examination including body weight;
- A urine pregnancy test will be completed in women of childbearing potential before administration of the dose. If the pregnancy test is positive, it must be confirmed with a serum pregnancy test.
- ECOG PS;
- Vital signs;
- ECG (predose only);
- CCI
- Blood samples (to assess hematology, chemistry, and coagulation);
- Urinalysis;
- Serum AFP;
- AE assessment;
- Recording of concomitant medications/procedures;
- FHSI-8 and FACT-HP (Phase II only).

# 7.1.3.5 Cycle 2 Day 8

This visit may be performed within  $\pm 5$  days of Cycle 2 Day 8. The following assessments and examinations will be performed on this day:

- Physical examination including body weight;
- Vital signs;
- Blood samples (to assess hematology, chemistry, and coagulation);
- AE assessment;
- Recording of concomitant medications/procedures;
- FHSI-8 and FACT-HP (Phase II only).

# 7.1.3.6 Cycle 2 Day 15

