### 7.5.2 Pharmacokinetic Calculations

The following PK parameters will be calculated and summarized from the measured individual plasma concentrations of MSC2156119J using noncompartmental methods based on frequent PK sampling as applied in Phase Ib.

- Cmax: observed maximum plasma concentration
- Cmin: observed minimum plasma concentration
- Cav: average plasma concentration within 1 dosing interval
- tmax: time to reach maximum plasma concentration
- AUC0-t: area under the plasma concentration versus time curve from time zero to the last sampling time t at which the concentration is at or above the lower limit of quantification. AUC0-t will be calculated according to the mixed log-linear trapezoidal rule
- AUC0-tau: area under the plasma concentration versus time curve within 1 dosing interval

Further derived PK parameters will be calculated, when appropriate:

- $\lambda_z$ : apparent terminal rate constant determined by log-linear regression analysis of the measured plasma concentrations of the terminal log-linear phase
- $t_{1/2}$ : apparent terminal half-life, calculated by  $ln2/\lambda_z$
- AUC0-∞: area under the plasma concentration versus time curve from time zero to infinity. AUC0-∞ will be calculated by combining AUC0-t and AUCextra. AUCextra represents an extrapolated value obtained by Clast/λz, where Clast is the calculated plasma concentration at the last sampling time point at which the measured plasma concentration is at or above the lower limit of quantification. If the value of AUCextra provides more than 20% of AUC0-∞, this parameter and all related parameters (e.g., total body clearance of drug [CL] and volume of distribution associated to the terminal phase [Vz]) will be rejected as implausible and not included for further statistical analysis.
- CL/F: apparent body clearance of the drug from plasma,  $CL = Dose/AUC_{0-\infty}$
- $V_z/F$ : apparent volume of distribution associated to the terminal phase, calculated by  $Dose/(AUC_{0-\infty}*\lambda_z)$
- Vss/F: apparent volume of distribution at steady state
- CC

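### Phase Ib SAP: if the Day 15 24-hour sample is missed, the Cav fallback divides a 10-hour area by 24 hours and understates Cav by about 37–57%

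*SAP*

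**What the plan says.** Phase Ib SAP 16.2.2.2 describes Cav as "The average concentration at steady state, calculated on Cycle 1 Day 15 only". With its typesetting codes left in, the formula reads "C_{av} = AUC_{\tau}/\tau$ (AUC _{0-t} if necessary". No condition is given for when the fallback becomes necessary, and no other divisor is supplied.

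The same section defines AUC0-t as "Area under the concentration-time curve from time zero to the last quantifiable concentration". It accepts AUCτ when the sample at τ is less than 10% off time, and sets AUCτ to missing otherwise ("If actual time deviation is equal to or greater than 10" percent). PTF is 100 × (Cmax − Cmin)/Cav. Cmin and PTF are both described over a complete dosing interval. The section also rules out parameters that depend on λz and, apart from using the scheduled time when an actual time is missing, any further imputation.

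Protocol 7.5.2 defines Cav as the "average plasma concentration within 1 dosing interval". Dosing is once daily (Protocol 7.1.3: "MSC2156119J will be administered once daily over a 21 day cycle"), so τ is 24 h. The Day 15 schedule in Protocol 7.1.3.3 is "PK blood samples (predose and at 0.25, 0.5, 1, 2, 4, 8, 10, and 24 hours postdose; Phase Ib only". Cav is a named Phase Ib secondary PK endpoint (Protocol 8.3.2.2; Phase Ib SAP Table A). PTF is not on the protocol's list.

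**The concern.** AUCτ divided by τ is an average over one interval. AUC0-t divided by τ is an average over one interval only if t equals τ. The fallback is used when AUCτ is unavailable, and that is when t does not equal τ. The SAP therefore withholds AUCτ as unreliable and then builds Cav from a less suitable area over an unchanged divisor.

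The worst case is a missed 24 h sample, because nothing is drawn between 10 and 24 h. With no λz and no imputation, there is no route to a concentration at τ, so the only area available ends at 10 h. The result contradicts the protocol's definition of a named endpoint and can be arithmetically impossible for an average. Cohorts are small (3–6 subjects at 300 mg, up to 12 at 500 mg), so one such value can move a cohort summary.

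**Working it through.** The documents state no Cav or PTF value, so there is no plan figure to reproduce.

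**Inputs from the documents.** τ = 24 h. Day 15 times are 0, 0.25, 0.5, 1, 2, 4, 8, 10 and 24 h. AUC is linear-up/log-down. AUCτ is missing at a deviation of 10% or more: 0.10 × 24 = 2.4 h, so at or before 21.6 h, or at or after 26.4 h.

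**Assumptions, because the documents give neither quantity.** Half-life 8, 12, 24, 36 and 48 h; ka 0.2, 0.5 and 1.0 per h; one-compartment oral model at steady state. In units of F × dose/V, with ke = ln 2/half-life:

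C(t) = ka/(ka − ke) × [e^(−ke·t)/(1 − e^(−ke·τ)) − e^(−ka·t)/(1 − e^(−ka·τ))]

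**Model-free limit.** For a flat profile, AUC0-10/AUC0-24 = 10/24 = 0.417, so Cav is 58.3% too low. With the last sample at 27 h, 27/24 = 1.125, so Cav is about 12% too high.

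**Worked case, half-life 24 h, ka 0.5, 24 h sample missed.** On the sampling grid AUC0-24 = 34.47, AUC0-10 = 16.20, Cmax = 1.747 and Cmin = 1.061.

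- Intended Cav = 34.47/24 = 1.436. Fallback Cav = 16.20/24 = 0.675. Ratio 0.47, so 53% too low.
- Fallback Cav against observed minimum: 0.675/1.061 = 0.64, so the average lies below the minimum.
- PTF, if computed: 100 × (1.747 − 1.061)/1.436 = 48%, against 100 × (1.747 − 1.061)/0.675 = 102%.

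**Over the grid (ranges across ka).**

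| Half-life (h) | Missed: fallback Cav/true Cav | Missed: fallback Cav/observed minimum | Missed: PTF multiplier | 27 h sample: Cav ratio |
|---|---|---|---|---|
| 8 | 0.51–0.63 | 1.00–1.92 | 1.6–2.0 | 1.04–1.05 |
| 12 | 0.47–0.56 | 0.73–1.13 | 1.8–2.1 | 1.06–1.07 |
| 24 | 0.44–0.49 | 0.54–0.68 | 2.1–2.3 | 1.09 |
| 36 | 0.43–0.46 | 0.50–0.58 | 2.2–2.3 | 1.10 |
| 48 | 0.43–0.45 | 0.47–0.53 | 2.2–2.3 | 1.10–1.11 |

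Over a wider grid (half-life 6–120 h, ka 0.15–2 per h), a missed sample gives Cav 29–58% too low. At the edges of the 10% rule the error is small: 2–10% too low at 21.6 h and 2–10% too high at 26.4 h. For samples at 26.4–30 h the PTF multiplier is only 1.00–1.27.

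**Effect on a cohort summary.** With one affected subject at a ratio of 0.45, the geometric mean is multiplied by 0.45^(1/n): 0.94 for n = 12, 0.88 for n = 6, 0.77 for n = 3.

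**Dividing by t instead.** AUC0-10/10 equals the fallback ratio times 2.4: 0.428 × 2.4 = 1.03 to 0.628 × 2.4 = 1.51. That is 3–51% too high, because the 10 h window holds the peak and omits most of the decline.

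**The case against.** Several points on the other side are sound.

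- The only trigger the SAP spells out is a timing deviation. Near the 10% limits the error is 2–10%. The large figure needs the sample to be lost altogether.
- The SAP ties Cmin and PTF to a complete dosing interval. On a strict reading neither is computed without the 24 h sample, so no doubled PTF would be reported. The SAP does not state this suppression, and Cav carries no such wording, so the point limits the PTF claim but not the Cav claim.
- The SAP restricts evaluation to subjects with sufficient concentration-time data, and its Appendix 1 provides for PK-scientist review of exclusions. Sufficiency is undefined, so these may catch the problem but do not rule it out. The listing of sampling times and deviations would make affected subjects identifiable.

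A reader might infer three stronger things that the documents do not support.

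- **That a late sample also lowers Cav and doubles PTF.** It does the opposite to Cav and changes PTF little.
- **That the RP2D decision is distorted.** Protocol 5.1.2 makes the PK profile part of confirming the dose. But this SAP governs the final report, run after all subjects have stopped treatment and completed safety follow-up. SMC data are set by its charter and a separate SAP (Protocol 6.2.1.1 and 8.5.4.1). Dose proportionality and accumulation use AUCτ and Cmax, which the fallback leaves alone.
- **That the Day 15 24 h draw is obscure and likely to be missed.** It is in the Day 15 visit text and has its own row, with a ±30 min window, in Protocol Appendix I. Nothing indicates how many subjects would need the fallback.

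**Conclusion.** The rule is wrong as written for a named secondary endpoint. With the Day 15 24 h sample missed, Cav is about 37–57% too low under the assumed half-life of 8–48 h and ka of 0.2–1.0 per h. The direction and the 58% flat-profile limit do not depend on the model; the exact size does. For half-lives of about 24 h or more, the value lies below the subject's own observed minimum. PTF would be roughly doubled, but only if it were computed despite the complete-interval wording. A sample 10% or more late gives a smaller error upward: about 4–11% at 27 h, about 12% for a flat profile.

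The consequence is limited to descriptive PK summaries, with no planned hypothesis test, for affected subjects in small cohorts. The correction is worthwhile because the wrong result follows from a stated rule, but it does not bear on the trial's primary conclusions.

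**What to change.** In Phase Ib SAP 16.2.2.2, delete the parenthetical that permits AUC0-t in the Cav formula, and add one sentence: Cav and PTF are reported as missing whenever AUCτ is missing. Keeping AUC0-t and dividing by t is not an adequate substitute, as the working shows.

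Substituting the Day 15 predose value for the 24 h value, or interpolating to 24 h from a late sample, is not part of the required change. Either would need an explicit exception to the SAP's no-imputation rule, and interpolation would also need one to its 10% rule. A simulation that imposes steady state cannot validate predose substitution, since the two concentrations are then equal by construction.

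The cost is one edited line, one added sentence and a small change to the PK programming. No new samples are needed. The downside is a few missing Cav and PTF values in small cohorts.
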